6.0	Update KM confidence interval method	[name]
7.0	 Updated based on SAP template version C. Add section 2 for List of Abbreviations and Definitions of Terms Add section 5 for investigation section including study duration, inclusion/exclusion criteria Add 7.1.1 Disposition of Subjects Add 7.1.2 Clinical Investigation Plan (CIP) Deviations Add 7.5 adjustments for multiple comparisons Add 7.10 safety evaluation Add 7.11 Changes to Planned Analysis Add 8 Validation Requirements Updated SAP to reflect PERIGON pivotal trial CIP 1F Add TAV-in-SAV analysis population in the analysis set section in 7.1.3 	[name], Principal Statistician

2. List of Abbreviations and Definitions of Terms

Abbreviation	Definition
AE	Adverse Event
AVR	Aortic Valve Replacement
CABG	Coronary Artery Bypass Graft
CIP	Clinical Investigation Plan
EOA	Effective Orifice Area
EOAI	Effective Orifice Area Index
GFR	Glomerular Filtration Rate
НОСМ	Hypertrophic Obstructive Cardiomyopathy
LAA	Left Atrial Appendage
OPC	Objective Performance Criteria
PFO	Patent Foramen Ovale
РМА	Pre-market Approval Application
PVL	Paravalvular Leak
SAP	Statistical Analysis Plan
TAV in SAV	Transcatheter aortic valve implantation for a failing surgical
	bioprosthesis

3. Introduction

PERIGON Pivotal Trial is a prospective, interventional, non-randomized, worldwide, multi-site trial, with each center following a common protocol. The purpose of this trial is to evaluate the safety and efficacy of the Medtronic Model 400 bovine pericardial stented aortic bioprosthesis in a patient population undergoing surgical aortic valve replacement. All enrolled subjects will be assigned to aortic surgical valve replacement with the Model 400 Aortic Valve Bioprosthesis. The trial design is based on the recommendations of the FDA Heart Valve guidance document (2010) and EN ISO 5840:2009 standard for cardiac valve prostheses. This Statistical Analysis Plan (SAP) is designed to document, before data are analyzed, the rationale for the design of the study and the planned analyses that will be included in study reports, based on PERIGON Pivotal Trial Clinical Investigation Plan (CIP) version specified on the SAP cover page. This SAP does not limit the analysis in reports. Additional analysis of the trial data beyond this plan is expected.

4. Study Objectives

Safety objective: to evaluate the safety of the Model 400 valve with respect to valve-related adverse events and death

Effectiveness objective: to confirm the effectiveness of the Model 400 valve with regard to NYHA classification and hemodynamic performance.

Medtronic PERIGON Pivotal Trial Statistical Analysis Form Plan Medtronic Revision 7.0 Page 5 of 22

Safety Objective 4.1

The safety objective is to evaluate the safety of the Model 400 valve with regard to valve-related adverse events and death.

4.1.1 Endpoints

Safety of the valve will be evaluated by the time-related incidence of valve-related adverse events and death. The following valve-related adverse events will be evaluated in this trial: Thromboembolism, Thrombosis, Hemorrhage, Paravalvular leak (PVL), Endocarditis, Hemolysis, Structural valve deterioration, Non-structural dysfunction, Reintervention, Explant, and Death.

Effectiveness Objective 4.2

The effectiveness objective is to confirm the effectiveness of the Model 400 valve, with regard to NYHA Functional Classification and hemodynamic performance.

4.2.1 Endpoints

The effectiveness endpoints are

• NYHA Functional Classification (at discharge (or 30 days), 3-6 months, 1 year and annually thereafter through 5 years) is a classification system for defining cardiac disease and related functional limitations into four broad categorizations:

Class I	Subject with cardiac disease but without resulting limitations of physical activity. Ordinary physical activity does not cause undue fatigue, palpitation, dyspnea, or anginal pain.
Class II	Subjects with cardiac disease resulting in slight limitation of physical activity. They are comfortable at rest. Ordinary physical activity results in fatigue, palpitation, dyspnea, or anginal pain.
Class III	Subjects with cardiac disease resulting in marked limitation of physical activity. They are comfortable at rest. Less than ordinary physical activity causes fatigue, palpitation, dyspnea, or anginal pain.
Class IV	Subjects with cardiac disease resulting in inability to carry on any physical activity without discomfort. Symptoms of cardiac insufficiency or of the anginal syndrome may be present even at rest. If any physical activity is undertaken, discomfort is increased.

- Hemodynamic Performance (at discharge (or 30 days), 3-6 months, 1 year and • annually thereafter through 5 years) including
 - effective orifice area (EOA)
 - effective orifice area index (EOAI)
 - peak pressure gradient 0
 - mean pressure gradient 0

Medtronic PERIGON Pivotal Trial Statistical Analysis	Form
Revision 7.0 Page 6 of 22	Medtronic

- $\circ \quad \text{valvular regurgitation} \\$
- o performance index
- \circ cardiac output
- $\circ \quad \text{cardiac index} \\$

5. Investigation Plan

A maximum of 1300 subjects will be implanted at up to 40 sites with approximately 14 sites in Europe, 4 in Canada and up to 22 in the United States. Each implanted subject will be consented to be followed for 5 years, or until trial closure. A minimum follow-up of both 150 patients followed to 1-year and 400 patient-years will be completed to satisfy the requirements stated in EN ISO 5840:2009. A minimum follow-up of both 300 patients followed to 1-year and 800 patient-years will be completed to satisfy the requirements stated in the FDA Heart Valve Guidance. Total expected duration of the trial is approximately 8 years.

Patients who require aortic valve replacement (AVR) for any reason may be considered for this trial if they meet all of the inclusion and none of the exclusion criteria.

5.1 Inclusion Criteria

Patients must meet all of the following criteria to be included in the trial.

1. Patient has moderate or greater aortic stenosis or regurgitation, and there is clinical indication

for replacement of their native or prosthetic aortic valve with a bioprosthesis, with or without

concomitant procedures, which are limited to any of the following:

- LAA ligation
- CABG
- PFO closure
- Ascending aortic aneurysm or dissection repair not requiring circulatory arrest
- Resection of a sub-aortic membrane not requiring myectomy
- 2. Patient is geographically stable and willing to return to the implanting site for all follow-up visits
- 3. Patient is of legal age to provide informed consent in the country where they enroll in the trial
- 4. Patient has been adequately informed of risks and requirements of the trial and is willing and able to provide informed consent for participation in the clinical trial

5.2 Exclusion Criteria

- 1. Patients who meet any of the following criteria will not qualify for participation in the trial. Patient has a pre-existing prosthetic valve or annuloplasty device in another position or requires replacement or repair of the mitral, pulmonary or tricuspid valve
- 2. Patient has had previous implant and then explant of the Model 400 aortic valve bioprosthesis
- 3. Patient presents with active endocarditis, active myocarditis, or other systemic infection

Revision 7.0

Page 7 of 22

Medtronic

- 4. Patient has an anatomical abnormality which would increase surgical risk of morbidity or mortality, including:
 - Ascending aortic aneurysm or dissection repair requiring circulatory arrest
 - Acute Type A aortic dissection
 - Ventricular aneurysm
 - Porcelain aorta
 - Hostile mediastinum
 - Hypertrophic obstructive cardiomyopathy (HOCM)
 - Documented pulmonary hypertension (systolic >60mmHg)
- 5. Patient has a non-cardiac major or progressive disease, with a life expectancy of less than 2 years. These conditions include, but are not limited to:
 - Child-Pugh Class C liver disease
 - Terminal cancer
 - End-stage lung disease
- 6. Patient has renal failure, defined as dialysis therapy or GFR<30 mL/min/1.73 m2.
- 7. Patient has hyperparathyroidism
- 8. Patient is participating in another investigational device or drug trial or observational competitive study
- 9. Patient is pregnant, lactating, or planning to become pregnant during the trial period
- 10. Patient has a documented history of substance (drug or alcohol) abuse
- 11. Patient has greater than mild mitral valve regurgitation or greater than mild tricuspid valve regurgitation as assessed by echocardiography
- 12. Patient has systolic EF<20% as assessed by echocardiography
- 13. Patient has Grade IV Diastolic Dysfunction
- 14. Patient has documented bleeding diatheses
- 15. Patient has had an acute preoperative neurological deficit or myocardial infarction and has not returned to baseline or stabilized ≥30 days prior to enrollment
- 16. Patient requires emergency surgery

6. Determination of Sample Size

Sample size for this trial was based on the safety objective. Sample size calculations were not performed for the effectiveness objective.

6.1 Sample Size Methods and Assumptions

Adverse Event	Linearized Rate
	(% per Patient-year)
Thromboembolism	2.5
Valve Thrombosis	0.2

Table 1: OPC for Tissue Prosthetic Heart Valves

Medtronic PERIGON Pivotal Trial Statistical Analysis Plan		Form
Revision 7.0	Page 8 of 22	Medtronic
All Hemorrhage	1.4	
All Paravalvular Leak Major Paravalvular Leak	1.2 0.6	
Endocarditis	1.2	

The safety objective will be assessed by comparing linearized valve-related adverse event rates from subjects implanted with the Model 400 valve to acceptable linearized valve-related adverse event rates following valve replacement as defined by FDA in the Heart Valve Guidance 2010ⁱ and EN ISO 5840:2009ⁱⁱ as Objective Performance Criteria (OPC). The OPC for tissue valves (based on the linearized rate) are presented in Table 1.

Sample size estimation is based on the methods of Grunkemeier^{III}. The following are assumptions for the sample size estimate:

One-sided alpha = 0.05 Power = $1 - \beta = 80\%$ $2XR_{OPC} = 2.4\%$ $R_{Model400} = 1.2\%$

In the above expressions, $2XR_{OPC}$ and $R_{Model400}$ denote the Performance Goal (null hypothesis proportion) and true proportion, respectively.

If the endpoint event has a constant risk of $R_{_OPC}$ per patient-year, then the distribution of the number of endpoint events occurring during a fixed time of T patient-years is a random variable E with Poisson distribution of mean $\lambda = R_{_OPC} \times T$. Thus, the probability of observing n or fewer events during T patient-years is:

$$P_{\lambda}(E \le n) = \sum_{k=0}^{n} e^{-\lambda} \frac{\lambda^k}{k!}$$

To reject the null hypothesis of $R_{Model400} \ge 2 X R_{OPC}$, the number of events E occurring during T patientyears is less than or equal to the critical value of n_{cv} . The critical value of n_{cv} is determined by the selected Type I (α) and Type II (β) levels. That is:

$$\begin{cases} P_{2\lambda}(E \le n_{c\nu}) \le \alpha \\ P_{\lambda}(E \le n_{c\nu}) \ge 1 - \beta \end{cases}$$

Thus the amount of data required to test the null hypothesis using the acceptable adverse event rate of 1.2% per patient-year is approximately 800 patient-years using the Poisson distribution, an alpha level of 5% and at least 80% power.

If all subjects are enrolled within a one-year time frame, and followed for one year postoperatively, then a total of 556 implants are required, considering a 5% attrition rate (Grunkemeier 1994). Therefore, accounting for attrition and expected enrollment rates, up to 650 implants are expected to gain 800 patient-years. With CIP version specified on SAP cover page, up to 1300 subjects will be implanted to allow for continuing enrollment during the regulatory submission to commercialization time period, to avoid a significant interruption in access to surgeons of the latest surgical valve technology.

Medtronic PERIGON Pivotal Trial Statistical Analysis Form Plan Revision 7.0 Page 9 of 22 Medtronic

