7.1.1.4 Analysis Methods

Primary endpoint analyses for regulatory approval will be done on consecutive subjects, and according to the requirements of the guidance documents:

- ISO5840:2009: for regulatory submissions in geographies adhering to the ISO5840:2009 standards (minimum of 150 subjects with 1 year follow up and 400 patient years)
- FDA Heart Valve Guidance 2010 for US FDA PMA (minimum of 300 subjects with 1 year follow up and 800 patient years).

Early rates of adverse events will be calculated as the number of early adverse events divided by the total number of subjects, expressed as a percentage. Early events are events occurring on or before 30 days post-operative.

Linearized rates will be calculated as the number of late events divided by the cumulative late post-operative patient-years, expressed as a percentage. Late events are events occurring after 30 days post-operative. For those adverse events with OPC available, the linearized rates and their associated one-sided upper 95% confidence bounds will be compared to 2 x the OPC rate to show that they are within acceptable limits.

Kaplan-Meier survival analyses will also be performed to summarize the adverse event data.

In addition, control articles based on current literature of previously approved heart valves will be selected. Adverse event data from the control articles will be provided so as to inform the reader of the current state of heart valve technology, as expressed by articles in quality peer-reviewed journals, and allow additional evaluation of the Model 400 adverse event data.

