7.2.2.3 P-Values

The statistical test for the safety objective will be performed at one-sided α =0.05. All reported p-values greater than or equal to 0.0001 will be rounded to four decimal places. P-values less than 0.0001 will be displayed as "<0.0001."

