7.9.1.2 Hypothesis

The safety objective will be assessed by comparing linearized valve-related adverse event rates from subjects implanted with the Model 400 valve to acceptable linearized valve-related adverse event rates following valve replacement as defined by FDA in the Heart Valve Guidance 2010ⁱ and EN ISO 5840:2009ⁱⁱ as Objective Performance Criteria (OPC). The OPC for tissue valves (based on the linearized rate) are presented in Table 1.

The trial is designed to test the hypothesis that the true linearized adverse event rate for the Model 400 valve ($R_{Model400}$) is equal to or greater than twice the acceptable rate of commercially available tissue prosthetic valves (R_{OPC}). The null (H_0) and alternative (H_A) hypotheses are written as follows.

 $H_0: R_{Model400} \ge 2 X R_{OPC}$

 $H_A: R_{Model400} < 2 X R_{OPC}$

This document is electronically controlled Medtronic Business Restricted 056-F286, Statistical Analysis Plan Template CONFIDENTIAL Rev C

Medtronic PERIGON Pivotal Trial Statistical Analysis		Form
Revision 7.0	Page 18 of 22	Medtronic

Where $R_{Model400}$ is the linearized adverse event rate for the Model 400 valve and R_{OPC} is the acceptable rate of commercially available tissue prosthetic valves. To reject the null hypothesis demonstrates statistically that the rate for the Model 400 valve is less than two times the acceptable rate.

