7.9.1.3 Data Collection and Analysis Methods

7.9.1.3.1 Data Collection and Analysis

Adverse device effects and outcomes will be identified and reported by the Investigator at all visits. All deaths and endpoint related adverse events will be reviewed by the CEC.

Early postoperative events are defined as those occurring on or before 30 days post-operative. Late postoperative events are those occurring after 30 days post-operative.

Early rates of adverse events will be calculated as the number of early adverse events divided by the total number of subjects, expressed as a percentage.

The late events rates will be calculated using the linearized event rate methodology. That is, the rate will be the number of late events divided by the late post-operative patient-years. For those adverse events with OPC available, the linearized rates and their associated one-sided upper 95% confidence bounds will be compared to the Objective Performance Criteria (OPC) to show that they are within acceptable limits. Formally, the method introduced by Cox^{iv} which gives the relatively most accurate results^v will be used:

χ .95,2 n_e +1/2Y_T

where ne is the number of late events and YT is the late post-operative patient-years. If there is 0 events, the one-sided upper 95% confidence bound will be 0.

Kaplan-Meier survival analyses will also be performed to summarize valve-related adverse events and death. The Kaplan-Meier rate and the corresponding 95% confidence interval will be presented for each visit interval. In addition, number of subjects at risk, number of events, number of censored subjects and the Kaplan-Meier survival curve or event curve will also be displayed.

In addition, control articles based on current literature of previously approved heart valves will be selected. Adverse event data from the control articles will be provided so as to inform the reader of the current state of heart valve technology, as expressed by articles in quality peer-reviewed journals, and allow additional evaluation of the Model 400 adverse event data.

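### SAP 7.9.1.3.1 compares the primary safety bound with the OPC instead of 2 x OPC and sets it to 0 when there are no events; the 800 patient-year cutoff does not say total or late

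*SAP*

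**What the plan says.** **Sizing.** SAP 6.1 takes a true rate of 1.2% per patient-year, a null of 2.4% (2 x OPC), one-sided alpha 0.05 and 80% power. It asks for a critical event count that satisfies both error limits under the Poisson distribution, and concludes that the amount of data "is approximately 800 patient-years using the Poisson distribution, an alpha level of 5% and at least 80% power". Protocol 7.1.1.3 gives 800 without the qualifier. Both documents translate this into 556 implants with 5% attrition.

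**Hypothesis and level.** SAP 7.9.1.2 sets the null at 2 x OPC: "To reject the null hypothesis demonstrates statistically that the rate for the Model 400 valve is less than two times the acceptable rate". SAP 7.2.2.3 fixes the level: "The statistical test for the safety objective will be performed at one-sided" alpha of 0.05.

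**Decision rule.** Protocol 7.1.1.4 says the one-sided upper 95% bounds "will be compared to 2 x the OPC rate to show that they are within acceptable limits". SAP 7.9.1.3.1 says the same bounds "will be compared to the Objective Performance Criteria (OPC) to show that they are within acceptable limits". It defines the estimate so that "the rate will be the number of late events divided by the late post-operative patient-years", introduces the bound with "Formally, the method introduced by Cox", and adds: "If there is 0 events, the one-sided upper 95% confidence bound will be 0".

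**Cutoff.** SAP 7.2.2.1 cuts the PMA data at the first date with at least 800 patient-years and does not say whether the first 30 days count. Protocol 2.2 and 7.1.1.4 give 800 (FDA) and 400 (ISO) as minimum exposures.

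**The concern.** The sentence that turns the data into a pass or fail names a different threshold from the hypothesis, the sizing and the protocol. A programmer working from SAP 7.9.1.3.1 alone would run a test with almost no chance of success for a valve that performs exactly at the OPC. In the other direction, an upper 95% bound of 0 cannot come from finite exposure, and it declares success for any event with a zero count, however little follow-up there is.

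The time basis matters because the test uses only exposure after day 30. If 800 is counted from implant, the test has less information than the sizing suggests. Even at exactly 800 late patient-years, the stated alpha and power are not those of the planned bound for a 1.2% event.

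**Working it through.** **Inputs.** OPC, null and alternative rates: SAP 6.1 and protocol Table 8. Late events over late patient-years (Y): SAP 7.9.1.3.1. The Cox formula is broken in the available text and is read here as chi-square(0.95, 2n+1)/(2Y), with n late events.

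**1. The plan's figure.** Require P(E ≤ n | 0.024T) ≤ 0.05 and P(E ≤ n | 0.012T) ≥ 0.80. The smallest whole T is 811, with n = 12: alpha 4.95%, power 81.6%. That is 11/800 = 1.4% above 800, so the SAP's approximate figure reproduces.

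**2. Literal comparator, 1.2% event, Y = 800.** The bound must lie below 1.2%.
- 4 events: 16.919/1600 = 1.057%, pass.
- 5 events: 19.675/1600 = 1.230%, fail.
- Pass probability at a true rate of 1.2% (mean 9.6): P(E ≤ 4) = 3.8%.

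Against 2.4%, 12 events pass (37.652/1600 = 2.353%) and 13 fail (40.113/1600 = 2.507%). Pass probability at a true 1.2%: 82.8%.

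**3. Zero events.** With n = 0 the formula gives 3.841/(2Y) = 1.921/Y.
- Valve thrombosis has 2 x OPC = 0.4%. At Y = 400 the formula gives 0.480%, fail; the SAP's zero rule passes it.
- Probability of zero events at a true 0.4%: exp(−0.004 × 400) = exp(−1.6) = 20.2%.
- The formula passes once 1.921/Y < 0.004, that is Y > 480.2. At Y = 800 it gives 0.240% and passes anyway.

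**4. Total or late.** Assume uniform one-year accrual, one further year of follow-up and 5% annual attrition. Mean follow-up is then 1.4418 years, of which 0.0820 years fall in the first 30 days.
- Total: 556 × 1.4418 = 801.6 patient-years.
- Early: 556 × 0.0820 = 45.6.
- Late: 801.6 − 45.6 = 756 patient-years.

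The 556 implants therefore reproduce 800 as total exposure, not as the late exposure that the test uses.

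**5. Operating characteristics for a 1.2% event against 2.4%.**

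| Late patient-years | SAP 6.1 rule: n, alpha, power | Cox bound: n, alpha, power |
|---|---|---|
| 756 | 10, 2.8%, 69.7% | 11, 5.1%, 79.6% |
| 800 | 11, 3.15%, 74.1% | 12, 5.56%, 82.8% |
| 811 | 12, 4.95%, 81.6% | 12, 4.95%, 81.6% |

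At exactly 800 no critical value meets both limits: 11 lacks power and 12 exceeds 5%.

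**6. Other sized events.** At 800, Thromboembolism (n = 29: 4.3%, 97.8%) and All Hemorrhage (n = 14: 4.0%, 83.9%) meet both limits under either rule. At 735 late patient-years their Cox alphas are 5.8% and 5.2%. The figure of 735 is one result for late exposure on the date total time reaches 800, assuming 1000 implants over 2.5 years.

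**The case against.** The intended comparator can be inferred. Protocol 7.1.1.4, SAP 6.1 and SAP 7.9.1.2 all use 2 x OPC, and SAP 7.11 declares consistency with the protocol. A reader might conclude from the 3.8% that the trial was set up to fail; the documents do not support that, because the literal reading contradicts the SAP's own hypothesis. What remains is that a pre-specified decision rule should not have to be inferred.

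The zero-event example concerns valve thrombosis, which SAP 6.2 leaves out of the sizing, and the rule changes no verdict against 2 x OPC at 800. Both points stand. Even so, valve thrombosis has an OPC and falls under the same comparison, and 400 patient-years is a stated reporting minimum.

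On sizing, the SAP says approximately 800, 811 is within that, and 800 is also the FDA guidance minimum. A reader might infer that the trial is undersized or that 800 is wrong; neither follows. Nor does 5.56% discredit the Cox bound. It is a named approximation, and the excess is a discreteness effect. If final-report exposure were 3000 to 5500 late patient-years (an assumption), its alpha would range from 4.4% to 5.7% and average 5.0%, with power near 1.

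The PMA cutoff for sizes 19 to 27 mm has almost certainly passed, since protocol 1.2 reports FDA approval in July 2017. For that dataset only reporting can change. SAP 7.2.1 also applies the plan to the final report, so the wording of 7.9.1.3.1 is still in force.

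**Conclusion.** The main point holds: SAP 7.9.1.3.1 is wrong as written in two places. The comparator conflicts with the protocol and with the SAP's own hypothesis and sizing. Taken literally, it cuts the pass probability for a valve at 1.2% from 82.8% to 3.8% at 800 late patient-years. The zero-event bound is not a valid 95% bound. It matters against 2 x OPC below about 481 late patient-years, and at 400 it gives valve thrombosis a 20.2% false pass rate.

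The secondary point is one of definition and disclosure. The time basis of the 800 cutoff is unstated, and the implant calculation counts early time that the test excludes. At exactly 800 late patient-years the planned bound has alpha 5.56% and power 82.8% for a 1.2% event, slightly over the nominal level.

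It would be tempting to say that only All Paravalvular Leak and Endocarditis, the 1.2% events, are affected. Among the sized events that is true at 800, but not at lower late exposures such as 735.

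The Cox figures rest on the stated reading of the formula. The 756 and 735 figures rest on assumed accrual and attrition. The comparator conflict rests on the text alone.

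**What to change.** 1. **SAP 7.9.1.3.1, comparator.** State that the bounds are compared with *2 x the OPC rate*, matching protocol 7.1.1.4 and SAP 7.9.1.2.
2. **SAP 7.9.1.3.1, zero events.** Delete the bound of 0 and use the formula value, 1.921/Y for the Cox bound.
3. **SAP 7.2.2.1.** Define any cutoff still to come in late patient-years (after day 30). For the PMA dataset, report the late patient-years actually used.
4. **SAP 6.1 and protocol 7.1.1.3.** Keep approximately 800 as the sizing figure and add the planned bound's properties at 800 late patient-years: rejects with 12 or fewer events, alpha about 5.6%, power about 83%. Note that this alpha slightly exceeds the one-sided 0.05 of SAP 7.2.2.3.

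Items 1, 2 and 4 are wording only. Item 3 needs no extra patients: under the accrual patterns checked (556 implants in 1 year up to 1300 in 3 years, 5% attrition), 800 late patient-years is reached about 32 days after 800 total. Moving to 800 late does not by itself meet both limits for a 1.2% event, so item 4 is needed as well. An exact Poisson bound, or a cutoff of 912 late patient-years (from which the exact rule meets both limits at every whole exposure checked, up to 6000), is optional and not part of the required change.
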